6.3. Blinding

Patients will be blinded to the group assignment. Nitrous oxide is a colorless and odorless gas which makes it unlikely for patients to identify the group assignment. Likewise, the study setup will be identical for both sessions, which will make an inadvertent unblinding of the study unlikely. The team responsible for the administration of the nitrous oxide treatment will be aware of the treatment assignment. This team is completely separate from the team assessing the study outcomes, which will be blinded to the group assignment. After the completion of each stage, patients will be asked to assess if they received active treatment or placebo using a Blinding Questionnaire. Responses will be recorded with a 5 point scale asking participants to rate the extent to which they knew they were exposed to nitrous oxide; 1) strongly believe the treatment was nitrous oxide, 2) somewhat believe the treatment was placebo, 4) strongly believe the treatment is placebo, and, 5) don't know.

6.4. Setting

The study will be performed in ECT suite at Barnes-Jewish Hospital or The Clinical Research Unit (CRU) suite within Washington University. The procedure room is equipped with vital sign monitoring and resuscitation equipment and devices and oxygen wall outlets. As part of the standard setup, a mobile FDA-approved breathing circuit will be used for this study or a nitrous oxide tank will be attached to the anesthesia machine.

6.5. Administration of Study Treatment

Except for the choice of gas mix (nitrous oxide or nitrogen [inert] placebo; both mixed with 50% oxygen) treatment sessions will be identical. The gas mix will be administered via a standard anesthesia facemask through tubing connected to the anesthesia machine or via a facemask which is connected via hose to an FDA-approved Porter/Praxair MXR breathing circuit. Total gas flow will be 2-8 L/min and nitrous oxide concentration will be titrated over the first 10 minutes to a maximum of 50%. Patients will be monitored during and after the treatment according to American Society of Anesthesiologists standard which include continuous 3-lead ECG, pulse oximetry, non-invasive blood pressure and end tidal CO₂ under the supervision of an attending-level anesthesiologist. After the one-hour treatment session, patients will be monitored for approximately an hour. A study team physician will determine if the patient meets criteria for discharge before the patient will be cleared to leave the research suite.

7. Data Collection and Analysis

7.1. Follow-Up

Assessments will be performed before and after (approximately 1 and 24 hours) each treatment, with the exception of the 3rd inhalation treatments in each Stage which will be monitored at approximately 72 hours from last inhalation session. Additional follow-up visits will be scheduled approximately one and two weeks following completion of the final gas inhalation session in any study stage (to assess for lasting efficacy of nitrous effects). However, only the two 24 hour and one 72 hour measures will be used in the statistical analysis of efficacy. The one and two week assessments will be performed to obtain preliminary information regarding lasting efficacy.

7.2. Assessment of Treatment Efficacy

The effects of the treatment will be assessed using standard scales used for mood assessments in psychiatry, psychosis, and disassociation:

- a) the MADRS (**Primary Outcome**) to assess change in depression;
- b) the Hamilton Depression Rating Scale-17 item (Ham-D17), secondary measure of depression;
- c) Young Mania Rating Scale (YMRS) to assess emergence of mania/hypomania (patients with YMRS scores > 12 will be removed from the trial and recommended for follow-up treatment per Psychiatry P.I., i.e., nitrous oxide treatments discontinued);
- d) the Profile of Mood States, 2nd edition (POMS 2) to assess for rapid/instantaneous changes in mood/affect;
- e) the Quick Inventory of Depressive Symptomatology- Self Report (QIDS –SR) patient-rated depression measure;
- f) Clinician Administered Dissociative States Scale (CADSS) for emergence of disassociation;
- g) the Brief Psychiatric Rating Scale (BPRS) to assess psychotic or hallucinogenic behavior; and
- h) Scale for Suicidal Ideation (SSI) to assesses for emergence of suicidal thinking.

Patients will be assessed approximately 30 minutes before treatment, and approximately 1 hour and 24-72 hours after treatment by one of the expert psychiatry study team members who will be blinded to the study group assignment.

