7.3. Assessment of Treatment Safety

Treatment safety will be assessed at several levels:

(1) Psychiatric AEs, such as psychotic symptoms or suicidal ideation, will be assessed via clinical interview as well as via standard scales. Emergence of psychosis will be identified by an increase in psychotic symptoms on the BPRS (for psychotic symptoms); suicidal ideation/intention will be assessed clinically and via the suicide question on the QIDS-SR (question #3) and the Scale for Suicidal Ideation (SSI) and recommended for additional follow-up treatment per Psychiatry P.I.

(2) Cardiovascular, respiratory and other AEs, will be identified clinically by continuous monitoring during and after the treatment. Follow-up recommendations will be given as needed, if necessary, by study personnel.

8. Data and Safety Monitoring

- 8.1. In general, the PIs have developed a specific set of Standard Operating Procedures (SOPs) for clinical research. All individuals working under the PI are required to read and be familiar and compliant with the SOPs. The PI's SOPs are in part developed from and are compliant with the Institutional guidelines, including those for a) Interactions with the Washington University Human Research Protection Office, b) Informed Consent Development and Implementation, c) Subject Recruitment and Screening, d) Subject Management While on Study, and e) Adverse Event Reporting.
- 8.2. The specific monitoring plan for this study is commensurate with the risks and the size and complexity of the investigations planned. The potential risks are attributable to the use of nitrous oxide and the underlying condition (bipolar depression). Based on these considerations the monitoring plan involves a **full DSMB** including an attending anesthesiologist knowledgeable in nitrous oxide pharmacology, an attending psychiatrist knowledgeable with an expertise in bipolar depression, and a biostatistician. All three members are not part of the study team. All reports of a Serious Adverse Event or an Unexpected Adverse Event will be investigated by the DSMB and reported to the IRB.

9. Data Analysis

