The primary outcome variable is the change from baseline in MADRS scores during the first study week in each Stage of the SPCD study. Stage-wise test statistics representing the active vs. placebo response will be combined with equal weights for each Stage. The full analysis set is defined as all patients who were randomized and had at least one treatment dose as well as one post-baseline efficacy assessment in Stage 1. In Stage 2, the placebo non-responders who were re-randomized and had at least one treatment dose as well as one post-baseline efficacy assessment contribute to the full analysis set. A mixed model for repeated measurements (MMRM) with an unstructured variance-covariance matrix will be used for the primary efficacy analysis. This direct likelihood model is the missing data handling method recommended by the National Research Council of the National Academies of Science report on prevention and handling of missing data.

Secondary outcomes, expressed as change from baseline at 72 hours after the 3rd and final inhalation treatment will also be evaluated using the data from the full analysis set, consisting of all-comer participants from **Stage 1** and placebo non-responders in **Stage 2**. The secondary efficacy endpoints include changes in Ham-D17, Young Mania Rating Scale (YMRS), POMS, 2nd edition, and QIDS – SR. Intra- and inter-individual comparison of scores on depression scales will be done using a repeated-measures mixed effects model.

Based on our pilot study where we saw a significant reduction in depression scores among 20 unipolar depressed patients, we decided to enroll 64 patients in this trial which is similar (or larger) than previous studies of rapid antidepressants in this patient population.

10. Risk Assessment

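### The rule for YMRS > 12 does not say that ratings continue, so the 72-hour YMRS endpoint may be missing or undefined in the patients with the highest earlier scores

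*Combined protocol and SAP*

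**What the plan says.** Section 7.2 includes the YMRS to detect emergent mania or hypomania and sets a stopping rule: patients with "YMRS scores > 12 will be removed from the trial and recommended for follow-up treatment per Psychiatry P.I., i.e., nitrous oxide treatments discontinued". The sentence first speaks of removal and then explains it as stopping the gas.

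On rating times, section 7.2 says "Patients will be assessed approximately 30 minutes before treatment, and approximately 1 hour and 24-72 hours after treatment". Section 7.1 ties ratings to treatments, puts the rating after session 3 at about 72 hours, and adds: "Additional follow-up visits will be scheduled approximately one and two weeks following completion of the final gas inhalation session in any study stage". It also says that "only the two 24 hour and one 72 hour measures will be used in the statistical analysis of efficacy". The synopsis (Study Design) gives a shorter list: baseline of each series, about 24 hours after sessions 1 and 2, and about 72 hours after session 3.

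Section 9 lists YMRS change among the secondary efficacy endpoints, which are "expressed as change from baseline at 72 hours after the 3rd and final inhalation treatment". It names a direct-likelihood repeated-measures model for the primary analysis and a mixed model for the depression scales. It does not clearly name a model for the YMRS.

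No section says that a patient who exceeds 12 is rated through to the endpoint visit, and none defines an early-termination visit.

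**The concern.** The stopping rule and the endpoint use the same scale. If the rule also ends ratings, the patients who lose the 72-hour YMRS are by construction those with the highest earlier YMRS. The remaining patients could then show little mania because those who developed it are no longer measured.

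Aim 1.2 is tolerability, and the YMRS is the only listed scale assigned to emergent mania or hypomania. At stake are the 72-hour YMRS comparison between arms and a scheduled record of how the mania runs after the gas stops. Stopping the gas and the threshold of 12 are not questioned.

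**Working it through.** **Inputs.** N = 64, with 25% active and 75% placebo in Stage 1 and 1:1 re-randomization of Stage 1 placebo patients (synopsis; sections 6.1 and 6.2). Sessions are every other day, for example Monday, Wednesday and Friday. With the first session as day 0, they fall on days 0, 2 and 4.

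**Arm sizes.** 64 × 0.25 = 16 and 64 × 0.75 = 48, which matches the approximate 48 in section 6.1. 48 / 2 = 24 per re-randomized Stage 2 arm.

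**Where a patient can first exceed 12 within a stage.** The table takes the widest schedule (sections 7.1 and 7.2) and assumes that the YMRS is given at every listed rating, which no section confirms. The rating before session 1 is not counted because no dose has been given in that stage. The efficacy measures are those on days 1, 3 and 7.

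| Rating that triggers | Day | Admitted to efficacy analysis (7.1) | On synopsis schedule | Efficacy measures lost under removal (of 3) |
|---|---|---|---|---|
| Session 1 + 1 h | 0 | no | no | 3 |
| Session 1 + 24 h | 1 | yes | yes | 2 |
| Session 2 pre | 2 | no | no | 2 |
| Session 2 + 1 h | 2 | no | no | 2 |
| Session 2 + 24 h | 3 | yes | yes | 1 |
| Session 3 pre | 4 | no | no | 1 |
| Session 3 + 1 h | 4 | no | no | 1 |
| Session 3 + 72 h | 7 | yes | yes | 0 |

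- Widest schedule: 7 trigger points before the 72-hour visit. At 5 of them the triggering score is not an admitted measure (4 of 6 if no 1-hour rating follows session 3, which section 7.1 leaves unclear).
- Synopsis schedule: 2 trigger points, days 1 and 3, both admitted. A repeated-measures model would then have every triggering score.

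**Removal reading.** A trigger at any of these points loses the 72-hour YMRS. A first score above 12 at the 72-hour visit loses nothing.

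**Gas-only reading.** The 24-hour rating after a session already given and the one- and two-week visits stay scheduled. But 6 of the 7 points (2 of 2 on the synopsis schedule) come before session 3, and the endpoint is dated from session 3. Suppose the later visits are counted from the last session received. They then fall on days 7 and 14 for a patient stopped after session 1 (0 + 7, 0 + 14), and on days 9 and 16 after session 2 (2 + 7, 2 + 14). Even the day-7 visit would be a one-week visit, which section 7.1 keeps out of the efficacy analysis.

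**Share of endpoint values per patient lost.** With full enrolment and no other missing values: Stage 1 active 1/16 = 6.3%; Stage 1 placebo 1/48 = 2.1%; Stage 2 re-randomized arm at least 1/24 = 4.2%, and more if only placebo non-responders count, as section 9 has it.

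**Possible bias, on assumed values only.** The documents give no YMRS distribution. A simulation removed patients who exceeded 12 at either 24-hour rating, taking a baseline mean of 4.

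- Concentrated switching (SD 3, correlation 0.5; 10% of active and no placebo patients rise by 12 points): true 72-hour difference 1.19, completers 0.05, regression on earlier scores 0.52. With a rise of 8 points: 0.79, 0.34 and 0.62.
- Even shift of all active patients by 2 or 4 points (SD 3 to 5, correlation 0.5 or 0.7): bias at most about 0.1 points.

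The selective loss follows from the removal wording. The size of the bias follows from the assumptions.

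**The case against.** The strongest reply is that the sentence explains itself: removal is glossed as stopping the gas. Section 10.2 speaks expressly of withdrawing a subject from the study, so the plan has words for full withdrawal when it wants them. A reader might infer from 7.2 that the plan stops all ratings once YMRS exceeds 12. The gloss means that the documents do not support this as a settled fact. That stands. It does not close the gap, because under the gas-only reading the endpoint still depends on a third inhalation that an early-stopped patient never receives.

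A reader might also infer that emergent mania would go unrecorded. It would not. Crossing 12 is itself the recorded event, and the limit in section 7.1 applies to the efficacy analysis, not to safety reporting. Section 7.3 says "Psychiatric AEs, such as psychotic symptoms or suicidal ideation, will be assessed via clinical interview as well as via standard scales", and section 8.2 says "All reports of a Serious Adverse Event or an Unexpected Adverse Event will be investigated by the DSMB and reported to the IRB". What may be lost is the 72-hour change score and the scheduled later ratings.

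The count of 7 trigger points with 5 unanalysed should not be read as the plan's schedule. It is the upper end of a range whose lower end is 2, both analysed.

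Finally, section 8.1 refers to operating procedures for managing subjects on study. These may cover visits after discontinuation, but the documents do not show that they do.

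**Conclusion.** The point holds as an ambiguity with a selective consequence. Under the removal reading, the 72-hour YMRS is missing in patients who exceeded 12 earlier in the stage. Under the gas-only reading, it is undefined for those stopped before session 3. The number of trigger points per stage is 2 to 7, and each patient lost costs 2.1% to 6.3% of a Stage 1 arm's endpoint values.

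How many patients this affects is unknown, because no switch rate is given. The bias could be negligible or could hide most of a concentrated mania signal, and the documents cannot say which.

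A reader might infer damage to the primary analysis, since removal would also cost later MADRS ratings. That is not claimed: section 9 names a direct-likelihood model for that outcome, and the documents offer nothing from which to size an effect. The point concerns one secondary endpoint that bears on tolerability. It is a cheap improvement.

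**What to change.** In section 7.2, state that YMRS > 12 ends study gas only, with no further gas in Stage 2. YMRS, MADRS and adverse-event ratings then continue on that stage's planned calendar days (1, 3 and 7, then the one- and two-week visits on days 11 and 18), unless consent is withdrawn or visits are judged unsafe. Day 7 stands in for the 72-hour rating when session 3 was not given; the synopsis already names a day-7 follow-up for the primary outcome.

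Flag ratings taken after gas stopped or rescue care began. Report the number of patients with any post-dose YMRS > 12 by arm and stage, so that a treated mania is not hidden by a later low score. Leave the threshold and clinical care as they are.

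Cost: one or two sentences, one case-report-form flag and one table. Compared with removal, a stopped patient keeps 5 rating visits after a day-0 trigger, 4 after day 1 or 2, and 3 after day 3 or 4, all already on the schedule. The downside is that these visits must be held and some ratings will follow rescue treatment.

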7.3. Assessment of Treatment Safety

Treatment safety will be assessed at several levels:

(1) Psychiatric AEs, such as psychotic symptoms or suicidal ideation, will be assessed via clinical interview as well as via standard scales. Emergence of psychosis will be identified by an increase in psychotic symptoms on the BPRS (for psychotic symptoms); suicidal ideation/intention will be assessed clinically and via the suicide question on the QIDS-SR (question #3) and the Scale for Suicidal Ideation (SSI) and recommended for additional follow-up treatment per Psychiatry P.I.

(2) Cardiovascular, respiratory and other AEs, will be identified clinically by continuous monitoring during and after the treatment. Follow-up recommendations will be given as needed, if necessary, by study personnel.

8. Data and Safety Monitoring

- 8.1. In general, the PIs have developed a specific set of Standard Operating Procedures (SOPs) for clinical research. All individuals working under the PI are required to read and be familiar and compliant with the SOPs. The PI's SOPs are in part developed from and are compliant with the Institutional guidelines, including those for a) Interactions with the Washington University Human Research Protection Office, b) Informed Consent Development and Implementation, c) Subject Recruitment and Screening, d) Subject Management While on Study, and e) Adverse Event Reporting.
- 8.2. The specific monitoring plan for this study is commensurate with the risks and the size and complexity of the investigations planned. The potential risks are attributable to the use of nitrous oxide and the underlying condition (bipolar depression). Based on these considerations the monitoring plan involves a **full DSMB** including an attending anesthesiologist knowledgeable in nitrous oxide pharmacology, an attending psychiatrist knowledgeable with an expertise in bipolar depression, and a biostatistician. All three members are not part of the study team. All reports of a Serious Adverse Event or an Unexpected Adverse Event will be investigated by the DSMB and reported to the IRB.

9. Data Analysis

The primary outcome variable is the change from baseline in MADRS scores during the first study week in each Stage of the SPCD study. Stage-wise test statistics representing the active vs. placebo response will be combined with equal weights for each Stage. The full analysis set is defined as all patients who were randomized and had at least one treatment dose as well as one post-baseline efficacy assessment in Stage 1. In Stage 2, the placebo non-responders who were re-randomized and had at least one treatment dose as well as one post-baseline efficacy assessment contribute to the full analysis set. A mixed model for repeated measurements (MMRM) with an unstructured variance-covariance matrix will be used for the primary efficacy analysis. This direct likelihood model is the missing data handling method recommended by the National Research Council of the National Academies of Science report on prevention and handling of missing data.

Secondary outcomes, expressed as change from baseline at 72 hours after the 3rd and final inhalation treatment will also be evaluated using the data from the full analysis set, consisting of all-comer participants from **Stage 1** and placebo non-responders in **Stage 2**. The secondary efficacy endpoints include changes in Ham-D17, Young Mania Rating Scale (YMRS), POMS, 2nd edition, and QIDS – SR. Intra- and inter-individual comparison of scores on depression scales will be done using a repeated-measures mixed effects model.

Based on our pilot study where we saw a significant reduction in depression scores among 20 unipolar depressed patients, we decided to enroll 64 patients in this trial which is similar (or larger) than previous studies of rapid antidepressants in this patient population.

10. Risk Assessment

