Statistical Methodology	Comparison of scores on MADRS by repeated-measures mixed model

1. Specific Aims

- 1.1. To determine if nitrous oxide is an efficacious treatment for treatment-resistant bipolar depression.
- 1.2. To obtain data about the tolerability of nitrous oxide in this setting.

2. Background

Bipolar Disorder (BPD) is characterized by alternating periods of sustained elevation in mood (manic episodes) and decreased mood (depressive episodes) intermixed with euthymia. Historically, considerable research effort has been put towards treating the manic phase of BPD, while relatively little emphasis has been placed on the depressed phase of the illness (1, 2). While the emphasis has been on the manic phase of BPD, phenomenology studies of BPD demonstrate that the depressed phase predominates the overall time spent in mood dysregulation and is responsible for more psychosocial impairment (3, 4). Further, evidence demonstrates that a significant percentage (as high as 40%) of BPD patients suffering from the depressive phase are treatment resistant (5-7). In fact, meta-analyses suggest that in the depressed phase approximately 25% of BPD patients will respond to the addition of an adjunctive antidepressant (8).

Recently ketamine, an antagonist of the N-methyl-d-aspartate (NMDA) subtype of glutamate receptors, has been shown to produce a rapid antidepressant effect in patients with treatment-resistant unipolar depression after a single infusion of 0.5 mg/kg over 40 minutes (9-11). More recently, two studies have demonstrated similar antidepressant effects of ketamine in treatment resistant bipolar depression (12, 13).

Although these ketamine trials offer substantial promise in treating treatment-resistant bipolar depression, ketamine has several well-established side effects that may limit its clinical usefulness. These include dissociative symptoms, hallucinations, delusions, the possibility of precipitating mania in patients with BPD and significant sympathetic nervous system activation. In addition, administration of ketamine typically requires intravenous access and supervision by a physician experienced in sedation. These side effects render ketamine a less than ideal antidepressant, despite its favorable effects.

Preliminary Data

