Nitrous oxide (laughing gas) is a colorless, odorless gas. Nitrous oxide is the oldest and most widely used FDA-approved anesthetic gas. The onset as well as offset of effect is within a few minutes. In this study we will use a mix of 50% nitrous oxide and 50% oxygen (nitrous) or 50% nitrogen/50% oxygen (placebo). This concentration (commonly used by dentists) avoids hypoxia and ideally achieves only mild to moderate sedation and is not sufficient to produce general anesthesia. Well-known side effects of nitrous oxide include: euphoria, sedation, nausea and vomiting, and inactivation of vitamin B₁₂ (commensurate with the duration of exposure and concentration used). Exposure to 50% nitrous oxide for 1 hour is considered extremely safe and has been well-tolerated in our preliminary studies. The use of nitrous oxide to treat treatment-resistant bipolar depression is off-label.

4. Eligibility

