6.1. Study Design (see summary figure below)

Prospective, randomized, placebo-controlled trial using the Sequential Parallel Comparison Design (SPCD) designed by PPD, a contract research organization. In the **first stage**, patients will be randomized (1:3 active [nitrous oxide] to placebo) to receive three 1-hour inhalation treatments every other day. Approximately 24-72 hours after the treatment session, patients will be assessed by the MADRS along with other scales as detailed below. Participants will also have follow-up visits/assessments performed approximately 1 and 2 weeks from the last inhalation session. The active treatment recipients from the **first stage** will receive a **second stage** of active treatment. All patients on placebo in the first stage (n \approx 48) will be re-randomized in the **second stage** (1:1 active to placebo) to three 1-hour treatments every other day, with the same follow-up visits/assessments as in Stage 1 (see study flow figure below). Throughout both stages group assignment will remain double-blinded to the participants and study raters conducting the assessments.

For ethical purposes, once the study blind has been broken those TRD subjects who were randomly assigned to receive successive placebo treatments will be offered an optional open label phase of active treatment (i.e., three 1-hour every other day inhalation treatments).

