10.1. Nitrous oxide

The side effects of nitrous oxide are well known to anesthesiologists. The dose (50%) and duration (1 hour) used in this protocol are considered very safe and low risk. Similar doses and durations are used in everyday dental practice without vital sign monitoring or supervision by a resuscitation-trained physician. With this dose of nitrous oxide, sedation may occur but not general anesthesia or respiratory depression. Minor side effects after nitrous oxide exposure such as nausea and vomiting may occur (and were observed in our preliminary study in unipolar depression), which are typically

self-limited and short. If a patient develops moderate to severe nausea and vomiting, we may administer 4mg of ondansetron. Other risks include euphoria, anxiety and increased heart rate.

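### Non-psychiatric adverse events are actively sought only until about one hour after each session, so delayed or cumulative effects rest on spontaneous report and may be under-counted

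*Combined protocol and SAP*

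**What the plan says.** Aim 1.2 in section 1 is: "To obtain data about the tolerability of nitrous oxide in this setting".

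Section 7.3 splits ascertainment in two. Psychiatric events are sought by clinical interview and by rating scales. All other events, under item (2), "will be identified clinically by continuous monitoring during and after the treatment". No second method is given for them. Section 6.5 fixes the end of that monitoring: "After the one-hour treatment session, patients will be monitored for approximately an hour", after which a study physician decides on discharge.

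Sections 7.1 and 7.2 bring participants back before each session, about 24 hours after sessions 1 and 2, about 72 hours after session 3, and about one and two weeks after the last session of a stage. The eight instruments in 7.2 cover depression, mania, mood state, dissociation, psychosis and suicidality. Section 7.1 gives lasting efficacy as the purpose of the one- and two-week visits.

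On exposure, section 6.1 randomises patients in Stage 1 "to receive three 1-hour inhalation treatments every other day", and sections 6.1 and 6.2 keep Stage 1 active patients on active treatment for a second series of three. Section 3 lists vitamin B12 inactivation as a known effect, "commensurate with the duration of exposure and concentration used". Section 10.1 states: "The dose (50%) and duration (1 hour) used in this protocol are considered very safe and low risk". Section 9 plans no analysis of adverse events or tolerability.

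**The concern.** Once the participant leaves the suite, continuous monitoring has ended and nothing in the plan asks about non-psychiatric events. Vomiting at home, or sedation noticed the next day, enters the data only if the participant mentions it and someone records it. Effects that build up over repeated sessions are in the same position.

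Tolerability is one of only two stated aims, and expected, non-serious events make up most of a tolerability profile. Incomplete capture lowers the absolute event rates. If capture is equally incomplete in both arms, it also shrinks the difference between nitrous oxide and placebo. Both effects flatter the drug. A clean record would be read as evidence of good tolerability over three or six sessions when it might partly reflect that nobody asked.

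**Working it through.** The plan states no event rate, capture rate or precision target for safety, so it has no figure of its own to reproduce. The check sets the passages side by side, counts the exposed patients, and then shows how capture would change what the data can exclude.

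**1. What is sought, and when**

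| Time | Psychiatric events | Other events |
|---|---|---|
| During gas and about 1 h after | scales and interview (7.2, 7.3) | continuous monitoring (7.3, 6.5) |
| Before later sessions, 24 h, 72 h | scales and interview | nothing specified |
| 1 and 2 weeks | assessment for lasting efficacy (7.1) | nothing specified |

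The word *after* in 7.3(2) cannot reasonably stretch to later days, because continuous monitoring stops at discharge.

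**2. Who is exposed, and how much**

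Inputs: N = 64 (section 5), and 1:3 then 1:1 allocation (6.2).

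- Stage 1 placebo: 64 × 0.75 = 48, which matches the figure of about 48 in 6.1.
- Active in both stages: 64 × 0.25 = 16 patients, 6 sessions × 1 h = 6 h each.
- Placebo then active: 48 / 2 = 24 patients, 3 sessions × 1 h = 3 h each.
- Placebo in both stages: 24 patients, 0 h in the blinded stages.
- Exposed in the blinded stages: 16 + 24 = 40.

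This assumes no drop-out and re-randomisation of all Stage 1 placebo patients. Optional open-label sessions would be extra.

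**3. What incomplete capture does (illustration)**

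Let c be the share of delayed events that reach the record. The documents do not give c, so a range is shown.

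With zero recorded events in n patients, the exact one-sided 95% upper limit for the true rate is [1 − 0.05^(1/n)] / c.

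| c | n = 40 (all exposed) | n = 16 (six sessions) |
|---|---|---|
| 1 | 7.2% | 17.1% |
| 0.5 | 14.4% | 34.1% |
| 0.25 | 28.9% | 68.3% |

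For an assumed true delayed-event rate of 10%, expected recorded cases are 40 × 0.10 × c, and the chance of recording at least one is 1 − (1 − 0.10c)^40:

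- c = 1: 4.0 cases, 98.5%
- c = 0.5: 2.0 cases, 87.1%
- c = 0.25: 1.0 case, 63.7%

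**4. Direction**

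With equal capture in both arms, the observed risk difference is c × (rate on nitrous oxide − rate on placebo), which is smaller than the true difference whenever c < 1. If participants who believe they had nitrous oxide volunteer more, the difference could move the other way. The direction is therefore probable, not certain.

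**The case against.** The plan is not blind to later events. Participants are seen in person several times after discharge and can volunteer symptoms. Section 8.1 requires compliance with procedures on adverse event reporting, whose content is not in the documents. Section 8.2 has a DSMB that includes an anesthesiologist investigate every report of a serious or unexpected event. Section 4.2(j) excludes chronic cobalamin or folate deficiency. The plan also gives reasons to expect events near the session: offset within minutes (section 3), nausea that is usually short (10.1), and brief adverse events in the pilot (section 2). This is a small pilot with efficacy as its primary outcome.

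Much of this stands, and it rules out four stronger readings that a reader might infer.

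- *Delayed events are missed.* The documents show only that nothing prompts their report. Some will be volunteered.
- *Almost all events are lost.* Monitoring covers 3 × (1 h + 1 h) = 6 h of the 18 days (432 h) from first session to the two-week visit, or 1.4%. That is a share of clock time, not of events, and the plan expects events to cluster near the session.
- *Neurological harm from B12 inactivation will go undetected.* Section 3 names the inactivation and its dependence on exposure. No passage says that 3 to 6 hours of gas causes neurological symptoms.
- *The one-hour statements contradict the schedule, or 10.1 leans on the pilot.* One hour is the correct length of a session. Section 10.1 argues from dental practice and cites the preliminary study only for nausea and vomiting. The statements simply do not address cumulative exposure.

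What the objection does not supply is a method. The reporting procedures are named but not described, and the DSMB clause acts on reports of serious or unexpected events. Neither says how expected, non-serious, delayed events are to be found.

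**Conclusion.** The concern holds as a gap in ascertainment. As written, the plan actively seeks non-psychiatric adverse events only until about one hour after each session. Anything later depends on spontaneous report, across three or six nitrous oxide sessions, and may be under-counted. The likely effect is tolerability that looks better than it is, with the reservation on direction given above.

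The size cannot be computed from the documents. The figures above rest on assumed capture shares and an assumed 10% event rate, and they show only how far a clean record would weaken. The conclusion also assumes that the unseen procedures do not already require a standard question at return visits. If they do, the protocol needs only to say so.

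The primary efficacy analysis is untouched. The point is still worth acting on, because it bears directly on a stated aim and is cheap to close.

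**What to change.** - **Section 7.3(2).** State that non-psychiatric adverse events are collected from the first session through the two-week visit of each stage. Use one short standard form at every existing visit: an open question covering the time since the last visit, plus the side effects that the protocol already names, such as nausea, vomiting and sedation.
- **Who asks.** Have the participant complete the form, or have it asked by someone blinded to assignment, and keep the answers from the MADRS raters. Non-rating team members should not ask, because section 6.2 says they know the assignment, and elicitation could then differ by arm. Since 6.2 leaves few blinded staff apart from the raters, self-completion is the simpler route.
- **Section 9.** Add an adverse event summary for all treated patients, by gas received and number of active sessions (0, 3 or 6). Show any open-label sessions separately.
- **Sections 3 and 10.1.** Reconcile the one-hour exposure statements with the three- and six-session schedule in 6.1.

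The cost is a few minutes per visit at visits already held, and more minor events on record. There is also a small chance that symptom questions prompt participants to guess their arm. The blinding questionnaire in 6.3, asked after each stage, would give some indication of this.
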